7. ANALYTICAL PLAN AND STATISTICAL METHODS

7.1 General Considerations

All computations for statistical analyses will be performed using SAS® software, Version 9.4 or later. All SAS programs used in the production of statistical summary outputs will be validated with independent programming prior to finalization. In addition, all program outputs will be independently reviewed. The validation process will be used to confirm that all data manipulations and calculations were accurately done. Once validation is complete, a senior

statistical reviewer will perform a final review of the documents to ensure the accuracy and consistency with this plan and consistency within tables. Upon completion of validation and quality review procedures, all documentation will be collected and filed by the project statistician or designee.

If necessary, the statistical analytical plan and statistical methods section may be updated before the database lock. Any changes in statistical methods that may have an impact on the primary conclusions drawn from this clinical trial will be described in an amendment to the protocol. All other changes in the statistical plan will be described in the clinical study report (CSR). An explanation will be provided for deviations from the planned analysis.

7.2 Reporting Conventions

The following conventions will be applied to all data presentations and analyses:

- Continuous variables will generally be summarized by the number of patients with missing and non-missing values, mean, standard deviation, median, Q1 (quartile 1), Q3 (quartile 3), minimum, and maximum.
- Categorical variables will be summarized by the number and percentage of patients within each category. If not specified otherwise, the number of patients with non-missing values will be the denominator for percentage calculations. The number of patients with missing values will be presented.
- Confidence intervals will be reported as two sided at the 95% level.
- All mean and median values will be formatted to one more decimal place than the measured value.
- Standard deviation values will be formatted to two more decimal places than the measured value.
- Minimum and maximum values will be presented with the same number of decimal places as the measured value.
- For non-efficacy values the number and percent of responses will be presented in the form XX (XX %), where the percentage is in parentheses. Percentages will be rounded to

the nearest percent. In the case of a frequency of zero, the frequency and percentage will be presented as 0 rather than 0 (0%).

- Date variables will be formatted as DDMMYY for presentation

All the analyses will be run displaying Group (Group 1 vs. Group 2). All rates will be summarized using counts and percentages.

7.3 Definition of Baseline

Baseline is defined as the measurement closest to, but prior to, the administration of study drug. No reassignment of visits will be conducted.

7.4 Handling of Dropouts and Missing, Unused and Spurious Data

All data will be analyzed.

No imputation of missing data will be performed, and analyses will use the observed cases only.

Formal outlier testing will not be performed. Data identified as potential outliers after review will be reviewed to determine whether they are spurious.

Spurious data are data determined to be incorrect upon review of site documents. If data is deemed to be spurious, the spurious data and the reason for it being spurious will be documented by the Sponsor in a Note-to-file. Data identified as spurious will be treated as missing unless they can be definitively corrected. If spurious data is identified, sensitivity analysis may be performed to assess the potential impact of any missing data or outliers on trial results by including the spurious data.

7.4.1 Dates

Imputation of missing or partial dates is not expected, but if a complete date is required for calculations, the following algorithms will be applied:

- For the start date:
 - If year, month, and day are missing then use the minimum of the patient's first visit date or the consent date.
 - If either only month or month and day are missing then use January 1.

- If only day is missing, impute the first day of the month.
- For the end date:
 - If year, month, and day are missing then use the patient's last visit date.
 - If either only month or month and day are missing then use December 31.
 - If only day is missing then use the last day of the month.
 - Do not expand the record past the patient's last visit.
 - The original missing or partial date, the imputed complete date, and the indicator variable that indicates which dates were imputed will be retained in the database.

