7.11.1 Adverse Events and Infusion Related Reactions

All adverse events (AEs) will be coded using the Medical Dictionary for Regulatory Activities (MedDRA). A TEAE is defined as an AE that occurs (or worsens) during or after study drug administration and through Day 28 after administration of study drug.

An overview of all AEs will be provided that will include:

- Number of AEs, TEAEs, non-serious TEAEs, and Serious Adverse Events (SAEs)
- Number of TEAEs and SAEs related to study drug
- Number of TEAEs related to study drug with CTCAE grade ≥ 3
- Number of AEs and study drug related SAEs resulting in:
 - Death

- Subject discontinuation
- Study drug discontinuation

TEAEs, treatment-related TEAEs, TEAEs by CTCAE grade, TEAEs that lead to discontinuation of study drug, SAEs, and SAEs that lead to discontinuation of study drug, will be summarized by system organ class (SOC) and preferred term (PT).

A listing of all AEs will also be generated.

Infusion related reactions (IRR) will be summarized, and a descriptive summary of the duration of IRR will be provided. A listing of all AEs, including a separate listing for IRR, will also be generated.

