24 JAN 2023

- ^a For female subjects, a serum sample for a serum pregnancy test will be collected at screening and on Day 0 and Day 28.
- ^b Body mass index will be calculated at Screening only.
- ^c Vital sign measurements will include systolic and diastolic blood pressure, pulse, respiratory rate, and oral temperature (in degrees Celsius). Blood pressure and pulse will be measured after a resting period of at least 5 minutes in the supine position.
- ^d Vitals are only to be collected if they are found to be abnormal at dosing
- ^e 12-lead ECG is to be performed prior to study drug administration
- ^f Patients will be assessed for AEs occurring from the time of dosing through Day 28 (± 5 days)
- ^g Hematology assessments will include hemoglobin, hematocrit, erythrocyte count (red blood cells), differential leukocytes, platelet count, and total leukocytes (white blood cells).
- ^h Pathologic analysis of surgical specimens will take place from the conclusion of surgery and up to 10 days after

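### SAP 7.4.1 sets no floor at the dosing date, so a post-dose adverse event with a partial start date can be imputed to before dosing and lose TEAE status

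*SAP*

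**What the plan says.** SAP 7.4.1 opens with a condition: "Imputation of missing or partial dates is not expected, but if a complete date is required for calculations, the following algorithms will be applied". For start dates there are then three cases:

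- Day unknown: "If only day is missing, impute the first day of the month".
- Month unknown, with or without the day: "If either only month or month and day are missing then use January 1".
- Whole date unknown: "use the minimum of the patient's first visit date or the consent date".

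None of the three mentions adverse events or the dosing date. The only bound in the section is "Do not expand the record past the patient's last visit". It stands under the end-date rules and limits the late side, not the early side. The section also keeps the original partial date and an imputation indicator in the database.

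SAP 7.11.1 defines treatment emergence by timing: "A TEAE is defined as an AE that occurs (or worsens) during or after study drug administration". The same sentence closes the window at Day 28. Protocol Section 8 and footnote f to the SAP's schedule of events both start adverse event collection at dosing (Day 0). SAP Section 1 gives the SAP precedence over the protocol on analysis and reporting.

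**The concern.** The start-date rule always picks the earliest date compatible with what was recorded. That suits medical history or prior medication. For an adverse event in a single-dose study it ignores something already known, namely that a newly recorded event began on or after dosing. The imputed onset can then fall before Day 0, outside the trial's own collection window, and fail the timing test for a TEAE.

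Safety is a secondary objective, and SAP Table 1 names the incidence of TEAEs and SAEs first among its measures. A date rule that can drop real post-dose events from the TEAE summaries errs in the direction that makes the agent look safer.

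**Working it through.** The documents give no figure to reproduce, so the check applies the written rule to every possible dosing date.

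**Inputs.** The imputation rules are from SAP 7.4.1. The TEAE test is from SAP 7.11.1, with an imputed start on the dosing date counted as treatment-emergent. Two assumptions are not in the documents: dosing dates are uniform over a 365-day year, and TEAE status is derived from the imputed start. Where a window of onset days is shown, onset is uniform over it.

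**Example.** Take dosing on 15 March with the day of onset missing.

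- True onset 15 or 20 March: imputed to 1 March, before dosing, so TEAE status is lost.
- True onset 3 April: imputed to 1 April, after dosing, so TEAE status is kept.

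**Day missing, general case.** For onset *t* days after dosing, the imputed start precedes dosing when onset falls in the dosing month and dosing was not on the 1st. In a month of length *L* that is *L* − *t* − 1 dosing dates. Summed over 12 months this is 365 − 12*t* − 12 = 353 − 12*t*, valid for *t* = 0 to 27. At *t* = 28 February contributes none, the seven 31-day months give 2 each and the four 30-day months give 1 each: 14 + 4 = 18.

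| True onset | Dosing dates moved / total | Share |
|---|---|---|
| Day 0 | 353 / 365 | 96.7% |
| Days 0–3 | (353 + 341 + 329 + 317) / (4 × 365) = 1,340 / 1,460 | 91.8% |
| Days 0–10 | (11 × 353 − 12 × 55) / (11 × 365) = 3,223 / 4,015 | 80.3% |
| Day 14 only | 185 / 365 | 50.7% |
| Day 28 only | 18 / 365 | 4.9% |
| Days 0–28 | (28 × 353 − 12 × 378 + 18) / (29 × 365) = 5,366 / 10,585 | 50.7% |

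**Month missing.** The imputed start precedes dosing when onset is in the dosing year and dosing was not on January 1, which is 364 − *t* dates. Day 0: 364 / 365 = 99.7%. Days 0–28: (29 × 364 − 406) / 10,585 = 10,150 / 10,585 = 95.9%. With about 28 days of follow-up the month should nearly always be known, so this case is remote.

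**Whole date missing.** The imputed start precedes dosing whenever consent or the first visit came before Day 0.

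**Direction.** For a day- or month-missing date, the imputed start is never later than the true one. At the dosing boundary the rule can therefore move a post-dose event to before dosing, never the reverse. For true onsets in Days 0 to 28 it can only remove TEAEs.

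**With a floor.** Repeating the count with the imputed start set no earlier than dosing, when the known month or year allows it, gives 0% moved in both the day-missing and the month-missing case.

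**The case against.** The strongest reply is that the loss is inferred. The rule applies only when a calculation needs a complete date, and no sentence says the TEAE flag is computed from an imputed one. Events are collected from Day 0, and protocol 8.2 keeps conditions present at screening out of the record unless they worsen. Almost every adverse event record is therefore treatment-emergent by construction, and a programmer could flag it so without any date. This stands as a limit: the defect is conditional. It does not remove the point. Timing relative to dosing is the kind of calculation 7.4.1 addresses, and the SAP offers no other derivation.

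The SAP also has safeguards. Affected events remain in the all-AE listing and the overall AE count. The SAE summaries are not described as restricted to TEAEs. Infusion reactions are summarised separately in 7.11.1 and counted in 7.9.4. The imputation indicator makes a moved event traceable. An event that worsens after dosing still qualifies. All of this is correct, though a listing does not restore a TEAE rate.

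Three stronger readings are tempting and are not supported:

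- *All partially dated events leave the TEAE tables.* The arithmetic contradicts this: about half of day-missing onsets over Days 0 to 28 stay after dosing.
- *Early reactions are the ones most likely to be lost.* The 92% to 97% shares are conditional on a missing day. The protocol requires the onset date and checks patients straight after infusion and on the day of surgery, so early events may be the least likely to lack a day.
- *The Day 28 cut-off wrongly discards onsets on Days 29 to 33.* The SAP cut-off agrees with protocol Section 8, which ends monitoring at Day 28. The ± 5 days in the schedule footnote can be read as a visit window. Ending at each patient's last visit would make follow-up vary from 23 to 33 days between patients, which is a trade-off, not a correction.

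**Conclusion.** The point holds in a limited form. As written, the start-date rule can give a post-dose adverse event a pre-dose onset, which conflicts with the trial's own collection window. If the TEAE flag uses that date, the event loses TEAE status unless it is recorded as worsening after dosing.

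The shares depend on uniform dosing dates and, for the 51% figure, on onset spread evenly over Days 0 to 28. They describe events that already have a partial date and say nothing about how many there will be. That number is not given, so the effect on TEAE incidence cannot be estimated. Since the SAP does not expect such dates, it is probably small. The analysis is descriptive and the study is not powered for testing, so no formal conclusion turns on it. Low priority, but worth correcting because the rule is wrong in the cases where it would be used.

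**What to change.** Add a rule for adverse events to SAP 7.4.1:

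- If the known part of the start date is compatible with onset on or after dosing, and the end date is not before dosing, impute the later of the dosing date and the first day of the known period.
- If the start date is wholly missing and the end date is not before dosing, impute the dosing date.

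In the 15 March example, a day-missing March onset becomes 15 March, and a day-missing April onset stays at 1 April. It would also help to state in 7.11.1 that TEAE status is derived from the start date after this rule. The Day 28 limit in 7.11.1 can stay as it is.

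The cost is a few sentences of SAP wording and no new data, and SAP 7.1 allows such an update before database lock. The downside is that the TEAE count may rise slightly, including by an occasional event that in truth began earlier in the dosing month.

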7.5 Adjustment for Multiplicity

There are no planned adjustments for multiple endpoints or analyses.

7.6 Adjustment for Multiple Centers

Differences between study centers will not be incorporated into the statistical analyses for this study. There are no plans to analyze data within centers.

7.7 Patient Disposition

The number of screened patients will be summarized.

The number of enrolled patients will be summarized, along with the number and percentage of enrolled patients in all of the analysis populations, patients completing the study, patients withdrawing from the study and their primary reason for withdrawal, and the number of deaths, by Group and overall.

Data listings of patient disposition, screening failures, and patient assignment to analysis groups will be created.

7.8 Protocol Deviations

Protocol deviations are defined as any variation from the protocol, such as enrollment of a patient who did not meet all inclusion and exclusion criteria or failure to perform the assessments

and procedures within the required time frame, that are identified by the clinical research associate monitoring the study.

The number and percentage of patients with at least one major protocol deviation and the categories of the major protocol deviations will be summarized for the Safety population.

All protocol deviations will be provided in a listing.

7.9 Patient Characteristics

Unless otherwise noted, all patient characteristics will use the Safety population.

7.9.1 Baseline and Demographic Characteristics

All baseline characteristics will be summarized by each Group and overall for the Safety population. The following parameters will be summarized:

- Age (years)
- Race
- Ethnicity
- Sex
- Child-bearing Potential (if female)
- Height (cm)
- Weight (kg)
- BMI (kg/m^2)
- Karnofsky Performance Rating

No hypothesis testing is planned for baseline characteristics, so the analysis will be purely descriptive.

Data listings of baseline characteristics and demographics including Karnofsky Score will be created.

7.9.2 Medical History

Medical history will be summarized for all non-cancer related medical events, previous cancers, and previous anti-cancer therapies. Medical conditions will be coded using Medical Dictionary of Regulatory Activities (MedDRA) 23.0 dictionary or higher and summarized by System Organ Class (SOC) and preferred term (PT) in the Safety population. A listing for the variables above will also be generated.

7.9.3 Prior and Concomitant Medications and Procedures/Treatments

Prior and concomitant medication (as well as concomitant procedures/treatments) will be summarized by Group and overall in the Safety population. Medications will be coded with the World Health Organization (WHO) Drug Dictionary (B3 2021-09-01 DDE). Concomitant medications will be summarized by Anatomical Therapeutic Chemical (ATC) Classification System level 2 and 4 codes (ATC2 and ATC4). Procedures/treatments will be coded using MedDRA 23.0 or higher and summarized by SOC and PT. A medication, procedure, or treatment will be considered to be concomitant if its end date is after the date of study drug administration. Medications with a missing end date will also be considered concomitant. A medication with an end date prior to the date of study drug administration will be considered prior medications.

Listings for prior and concomitant medications / procedures will be provided.

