6.2 Pegsitacianine Administration (Days 0)

Predose procedures

- Confirm eligibility for the study and that medical information is complete
- Record weight and height and calculate BMI
- Discuss how the patient is feeling and their everyday activities
- Record vital signs
- Perform a 12-lead electrocardiogram (ECG) to check the heart activity during pre-operative screening
- Install an IV line
- Obtain blood for routine laboratory tests, including a pregnancy test for females who are capable of becoming pregnant
- Obtain blood, urine, or a breath test to test for alcohol. This test may be performed if relevant to the patient's medical history. If a urine or breath test is used and is positive, a blood test may be used to confirm the test results
- Record all medications taken since the Screening visit, including prescription, over-the-counter, and herbal medications

The Sponsor recommends the use of prophylactic diphenhydramine prior to study drug administration to decrease the possibility of an infusion-related reaction.

Dosing and postdose procedures

Procedures during and after dosing of pegsitacianine are summarized below:

- Dosing of pegsitacianine will be administered through an IV injection
Total dosing time will depend on the patient's body weight and total volume to be administered
- The following postdose assessments and procedures will occur after infusion of the study drug has been completed:
 - Record the patient's vital signs immediately after the infusion and 60 minutes afterward
 - Discuss any new or unexpected changes in how the patient is feeling
 - Record all medications they are taking, including prescription, over-the-counter, and herbal medications

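### SAP 7.9.3 gives no category to a medication that ends on the dosing date, so drugs given only on Day 0 drop out of both the prior and the concomitant summaries (minor)

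*SAP*

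**What the plan says.** All the classification rules are in SAP 7.9.3.

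- **Concomitant:** a medication, procedure or treatment is "considered to be concomitant if its end date is after the date of study drug administration".
- **Missing end date:** "Medications with a missing end date will also be considered concomitant". This sentence names medications only.
- **Prior:** "A medication with an end date prior to the date of study drug administration will be considered prior medications". This too names medications only.
- **Tables:** "Prior and concomitant medication (as well as concomitant procedures/treatments) will be summarized by Group and overall in the Safety population". The breakdown is by drug class: "Concomitant medications will be summarized by Anatomical Therapeutic Chemical (ATC) Classification System level 2 and 4 codes".
- **Listings:** "Listings for prior and concomitant medications / procedures will be provided".

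On the data side, Protocol 6.2 states: "The Sponsor recommends the use of prophylactic diphenhydramine prior to study drug administration to decrease the possibility of an infusion-related reaction". Appendix 1 of the protocol, footnote f, treats this premedication as optional. Before dosing, site staff are to "Record all medications taken since the Screening visit, including prescription, over-the-counter, and herbal medications". Protocol 6.2 also has medications recorded after the infusion, and Protocol 4.1 requires concomitant medication details to be entered in full in the eCRF.

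**The concern.** Both date rules are strict: one needs an end date later than dosing, the other an end date earlier than dosing. They compare dates, not clock times. An end date equal to the dosing date satisfies neither.

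In many trials this would be a rare edge case. Here the study drug is a single infusion on Day 0, and the sponsor recommends an antihistamine just before it. A one-off dose given that day starts and ends on the one date that the rules leave out. The same holds for any short treatment of an infusion reaction, since Protocol 4.3 says these reactions generally begin within 5 minutes of the start of the infusion.

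At stake is whether the concomitant medication table is complete for the drugs most closely tied to the infusion. A reader of that table could see low counts in the relevant drug-class rows with no sign that Day 0-only records had been excluded.

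**Working it through.** No figure in the plan is to be reproduced. The check is whether the rules cover every case, followed by a bound on how many patients could be affected.

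**Step 1. Coverage of the rules.** Let E be the end date and D the dosing date.

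| Case | Medication, as written | Procedure or treatment, as written | Medication, with *on or after* |
|---|---|---|---|
| E < D | prior | not concomitant; no prior rule | prior |
| E = D | **no category** | **not concomitant** | concomitant |
| E > D | concomitant | concomitant | concomitant |
| E missing | concomitant | no rule stated | concomitant |

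One of the four medication cases is unassigned. With the amended wording, each medication record falls in exactly one category.

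**Step 2. Does another section close the gap?**

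- SAP 7.4.1 only fills in missing or partial dates. It does not say how a complete end date equal to dosing is classed.
- The protocol requires medications to be recorded but gives no rule for separating prior from concomitant.
- SAP section 1 lets the SAP prevail on analysis and reporting, so the wording of 7.9.3 governs.

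**Step 3. Patients who could have an unclassified record.** Planned enrolment is about 60 (Protocol 9.1, SAP section 4).

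- *Diphenhydramine given only on Day 0.* Uptake u is not stated, so affected patients = 60 × u. For u = 0, 0.25, 0.5 and 1 this gives 0, 15, 30 and 60. The two middle values are illustrations only.
- *Same-day treatment of a reaction.* Protocol 4.3 puts reactions at about 1 in 3, so 60 × 1/3 = 20 patients are expected to have one. The central 95% range of a Binomial(60, 1/3) is 13 to 27. The share given a drug is not stated, so the number affected runs from 0 up to however many have a reaction. The 1-in-3 rate is carried over unchanged, although premedication is recommended in order to lower it.
- *Either.* The two sets overlap and cannot together exceed enrolment, so the range is 0 to about 60.

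**Step 4. From records to table rows.** SAP 7.2 counts categorical variables by patient. For a given drug class:

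shortfall in the row = patients whose only otherwise-countable drugs in that class end on Day 0

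A patient with another drug of the same class that continues past Day 0, or has no end date, is still counted. The shortfall in any row is therefore at most the number of patients in Step 3, and may be smaller.

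**The case against.** The case for leaving the text alone runs as follows. Most programmers would class a same-day record as concomitant by convention. The tables are descriptive. Which side of the boundary takes Day 0 is a matter of choice. No passage says that the premedication is a single dose or that reactions are treated with drugs, and Protocol 4.3 describes them as tending to be mild or moderate and short-lived.

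Much of this stands. It limits the size of the point and keeps it minor. It does not remove the gap: the SAP does not state the convention, literal code would drop the record, and SAP 7.1 calls for validation by independent programming, which needs one rule for both programs.

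A reader might infer more than the documents support:

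- *That safety results are undercounted.* They are not. SAP 7.9.4 and 7.11.1 summarise infusion reactions and adverse events separately from the medication flags.
- *That the same date problem mislabels treatment-emergent events.* That would require the imputation rules in SAP 7.4.1 to set the treatment-emergent flag. The SAP does not say that they do, and 7.4.1 does not expect partial dates.
- *That the omitted records are certain to appear in the listings, or certain to be lost from them.* SAP 7.9.3 names the same two categories for the listings and does not say whether they are built from the same flags. Either outcome is possible.
- *That a table row will be short by as many as 60 patients.* That figure is the ceiling, reached only if every patient has a Day 0-only drug in that class and nothing else in it.

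**Conclusion.** The point holds and is minor. As worded, SAP 7.9.3 assigns no category to a medication ending on the dosing date and does not count a procedure or treatment ending that day as concomitant. Nothing elsewhere in the two documents supplies the missing rule.

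Between 0 and about 60 patients could have an unclassified medication record. The width of that range reflects the absence of any stated uptake of premedication or rate of drug treatment for reactions. It rests on enrolment of about 60 and on such drugs having an end date of Day 0. Medications that continue past Day 0 or have no end date are unaffected.

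The consequence is confined to the descriptive medication and procedure tables, and to the listings if they use the same flags. The primary CSE analysis, the sensitivity, specificity and predictive values, and the adverse event and infusion-reaction summaries do not depend on it.

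**What to change.** In SAP 7.9.3, define a medication, procedure or treatment as concomitant if its end date is on or after the dosing date, or is missing or ongoing. Keep prior as an end date before the dosing date. The amended wording also gives procedures and treatments a rule for missing end dates, which they now lack.

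The cost is one reworded definition and a small programming change. No new data are needed, and SAP 7.1 allows this section to be updated before database lock.

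The downside is that drugs stopped on Day 0 before the infusion will also be counted as concomitant, which makes the table somewhat longer. The change completes the table but does not yield a premedication count, because summaries by drug class cannot separate prophylaxis from treatment of a reaction. It also leaves procedures that ended before dosing without a defined category, since the prior rule covers medications only.
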